| Day/Week | Day 0 | Weeks 0-4 | Weeks 5-19 | Week 20 |
| Initial comprehensive history and physical exam | X | | | |
| Focused history and physical exam | | | X (monthly) | X |
| Anthropometric assessment | X | | X (monthly) | X |
| Physical activity questionnaire (IPAQ) | X | | X (monthly) | X |
| Dietary Log | | X (weekly) | X (weekly) | x |
| FitBit activity data download | | X (weekly) | X (weekly) | X |
| Cardiopulmonary fitness testing (VO2 max) | X | | | X |
| Electrocardiogram (ECG) | X | | | |
| Laboratories | X | | | X |
| Stool sample | X | | | X |
| Urine pregnancy testing (if applicable) | X | | | |
| Genetic testing | X | | | |

| | | | | |
|---|---|--|-------------|-----------------------|
| Liver MRI-PDFF | X | | | X |
| PROMIS Quality of Life Assessment via iPad (completed under direct supervision of trained research personnel) | X | | X (monthly) | X |
| DXA body composition testing | X | | | X |
| Liver biopsy | | | | X (if sub-randomized) |

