3.2 Exclusion Criteria

- > 90 minutes/week of at least moderate intensity exercise over the previous three months as assessed by the Get Active Questionnaire (GAQ).
- Pregnancy
- BMI < 18 or > 45 kg/m²(16)
- Uncontrolled diabetes (changes in medication dosing over the previous three months or hemoglobin A1c $> 9\%$)(12)
- Active cardiac symptoms
- Severe medical comorbidities/psychiatric illness
- Decompensated cirrhosis (history of esophageal varices, ascites or hepatic encephalopathy)
- Cancer with life expectancy < 6 months
- MRI contraindications (severe claustrophobia, implanted ferrous metal)
- Other liver disease (positive hepatitis B surface antigen)
- Active weight-loss program participation or weight-loss supplement use
- Active substance abuse/smoking
- Inability to provide informed consent
- Institutionalized/prisoner
- Inability to walk > 2 blocks or $\frac{1}{4}$ mile
- Concurrent use of antiplatelet medications excluding aspirin 81 mg once daily as aspirin
- Non-English-speaking patients due to unavailability of translators for all visits/sessions

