4.4 Eligibility/screening of subjects N/A

5.0 Consent Process and Documentation

5.1 Consent Process

5.1.1 Obtaining Informed Consent

5.1.1.1 Timing and Location of Consent

Subjects will be invited for initial consultation performed by the study PI. Informed consent will take place at this consultation. Investigators must ensure that patients are clearly and fully informed about the purpose, potential risks, and other critical issues regarding clinical studies in which they volunteer to participate. Freely given written informed consent must be obtained from every subject prior to clinical study participation, including informed consent for any screening procedures conducted to establish subject eligibility for the study. The rights, safety, and well-being of the study patients are the most important

considerations and should prevail over interests of science and society. The consent process will occur in a private room in the Penn State Hershey Medical Center General Clinical Research Center (GCRC). The PI will carefully discuss the risks and benefits of study participation and review study procedures. The PI will make it clear that the subject's standard clinical care will not be affected in any way through participation or non-participation in the study. All questions will be answered prior to signing the informed consent document and the subject will verbalize understanding at the time of consent. The consent process will take approximately 15 minutes.

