Whole blood will be drawn in the Penn State Hershey GCRC (hours 730a-4p) by trained GCRC nursing or NASHFit research staff. Whole blood will be obtained and placed into the following tubes in the amounts described below [total nine teaspoons (tsp) of blood]:

- Three 3mL lavender (EDTA) top tubes (1.8 tsp)
- Two 4.5mL green (sodium heparin) top tubes (1.8 tsp)
- Three 6mL red top tube (3.6 tsp)
- Three 2.7mL blue (sodium citrate) top tubes (1.6 tsp)

Samples will then be delivered by NashFit study personnel to both the Clinical Laboratory for processing to serum and platelet poor plasma and also to [name] in the Institute for Personalized Medicine (IPM) for processing prior to transfer to the Endocrine Core Laboratory. Samples will be frozen and picked up from the Clinical Laboratories by IPM staff and brought to the IPM for storage and also the Genome Sciences and Bioinformatics Core for Taqman assay performance. Coded samples will be shipped through the IPM to [name], Associate Professor in University Park for metabolomics analysis. Results will be sent back to the IPM per standard IPM operating procedure. Stool samples will be obtained from the subject at home with a home collection kit and mailed directly from the subject to [name] (collaborator), Assistant Professor of Medicine, Juniata College. Stool samples will be processed, analyzed with 16S rRNA testing and stored in [name] laboratory.

Intervention Conditions: The aerobic exercise protocol is adapted from the landmark NASH-exercise trials by Sullivan *et al*(91) and Bacchi *et al*(92) that demonstrated the efficacy of exercise in improving intrahepatic fat and body composition but did not evaluate the effect on hemostasis and thrombosis risk. Once subjects have passed screening, they will be randomized 2:1 into either the exercise or control group respectively (two exercise subjects per one control subject) using a computer-generated randomized scheme in blocks of six by an independent statistician ([name] Public Health Sciences).

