8.0 Subject Numbers and Statistical Plan

8.1 Number of Subjects
We expect to enroll 42 subjects.

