8.2 Sample size determination
Subjects will be randomized into two treatment groups. This is an efficient study design with increased power and is appropriate for the proposed exercise intervention. The primary outcome will be change in PAI-1 following a 16-week exercise course. Secondary outcomes are described above. Baseline levels of PAI-1 are between 35-45 ng/mL.(72, 74-76) Estimates for change in PAI-1 following exercise regimens of between 3-8 months duration range between 23-37% with >30% reduction only reported in regimens >6 months long.(72, 74-76) De Gues *et al.*(75) found an initial 24.5% reduction as measured at four months in PAI-1 levels in thirty healthy adults aerobically exercising 2.5 hours per week. We expect the exercise intervention to result in a 23% reduction (9 ng/dL) in PAI-1. We expect no change in PAI-1 levels in the control arm. We conservatively determined power calculations utilizing the standard deviations in the literature (2.0 for no exercise group and 14.0 for the aerobic exercise group). We expect a 15-20% attrition rate;(94) to account for this we will enroll an additional six subjects.

Based on these assumptions and a 2:1 enrollment ratio with two subjects in the aerobic exercise arm to every one subject in the standard of care arm, a total study enrollment size of 28 subjects in the aerobic exercise arm and 14 in the standard of care arm will achieve 80.74% power to detect a difference in mean PAI-1 at sixteen weeks of at least 9 ng/mL, using a two-sided, two-sample unequal variance t-test with a significance level (alpha) of 0.05. A total study enrollment of **42 subjects** is planned.

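### A single fixed block size of six, printed in the protocol of an unmasked single-site trial, makes up to 28.9% of assignments deducible in advance by anyone who tracks them

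*Combined protocol and SAP*

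**What the plan says.** The protocol covers allocation in the Intervention Conditions paragraph of Section 7.2. Once subjects have passed screening, "they will be randomized 2:1 into either the exercise or control group respectively", "using a computer-generated randomized scheme in blocks of six by an independent statistician". One block size is given. The documents describe no varying sizes, no stratification and no means of releasing assignments, such as a central system or sealed envelopes.

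The surrounding facts are these:

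- **Size.** Section 8.1: "We expect to enroll 42 subjects". Section 8.2 plans 28 exercise and 14 standard-of-care subjects.
- **Who enrols.** Section 5.1.1.1: "Subjects will be invited for initial consultation performed by the study PI". Consent is taken at the same consultation.
- **Who sees the arms.** Under Section 7.2, study investigators examine subjects in both arms every month. Section 16.5 adds a weekly team meeting.
- **Masking.** None is described. The comparison is supervised exercise against usual care.
- **Sites.** Section 18 (multi-site research) is marked not applicable.
- **Order of baseline work.** Section 7.2 lists history, height and weight, laboratory tests and MRI-PDFF among the baseline measures after consent. It places VO2 max, DXA, waist, hip and skinfold measures after randomization. The visit schedule puts VO2 max and DXA on day 0 without saying which side of randomization they fall.

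**The concern.** An independent statistician protects how the list is made. That does not stop someone deducing the rest of a block from assignments already visible, when the block size is known and fixed. Once two controls have appeared in a block, every remaining place is exercise. Once four exercise subjects have appeared, every remaining place is control.

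Randomization follows consent and screening, so any bias would have to act through whom the team approaches, when consent is taken, and how eligibility is judged. Some criteria leave room for judgement, for example "Severe medical comorbidities/psychiatric illness" in Section 3.2. There is a possible motive, even a well-meant one: exercise subjects who miss sessions face extension or removal, so a motivated candidate may seem a better fit for a place known to be exercise.

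The kind of subject enrolled bears on the endpoint. The protocol itself says that PAI-1 depends on adiposity (Section 1.1) and that people with higher baseline PAI-1 gain most from exercise (Section 2.1). The sample size rests on an unadjusted two-sample comparison, and Section 8.3 names no covariates for its regression models. With 14 controls planned, a few steered enrolments could matter.

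**Working it through.** **Inputs.** Ratio 2:1, block size 6 (Section 7.2); N = 42, split 28:14 (Sections 8.1 and 8.2); difference 9 ng/mL, SDs 14.0 (exercise) and 2.0 (control), two-sided alpha 0.05, unequal-variance t-test (Section 8.2).

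**1. The plan's own figures.** 42 / 6 = 7 complete blocks, and 7 × (4 + 2) gives exactly 28:14. The stated power of 80.74% is reproduced with 22 + 11 = 33 evaluable subjects: SE = √(14²/22 + 2²/11) = 3.045, noncentrality 9/3.045 = 2.956, Satterthwaite df 22.7. Then 33/(1 − 0.20) = 41.25, which rounds up to 42 at 2:1. (28 + 14 evaluable would give 89.7%. That is a separate matter and does not affect this point.) The documents give no predictability figure.

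**2. Certain assignments with fixed blocks of six.** A 4:2 block has 15 equally likely orderings. An assignment is certain when one arm's quota in the block is already used up.

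| Certain assignments at end of block | 1 | 2 | 3 | 4 |
|---|---|---|---|---|
| Orderings | 8 | 4 | 2 | 1 |

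Mean = (8×1 + 4×2 + 2×3 + 1×4)/15 = 26/15 = 1.733 per block, and 1.733/6 = 28.9%. The closed form agrees: 4/(2+1) + 2/(4+1) = 1.333 exercise + 0.400 control. Over seven blocks that is 9.3 exercise + 2.8 control = 12.1 of 42. By position in the block, the chance of being certain is 0, 0, 6.7%, 20%, 46.7% and 100%.

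**3. Overall predictability with fixed blocks of six.** Always guessing the arm with more places left gives 67/15 = 4.47 correct of 6, or 74.4%, against 66.7% from the 2:1 ratio alone. A second measure is the share of assignment variance that past assignments predict. With m places left in the block it is (6 − m)/(5m). Averaged over m = 1 to 6 this is (1 + 0.4 + 0.2 + 0.1 + 0.04 + 0)/6 = 0.29.

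**4. Randomly mixed blocks.** Lists of 42 were simulated with sizes drawn at equal probability. The observer knows the set of sizes and every past assignment.

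| Block sizes | Certain | Best guess | Predictable variance |
|---|---|---|---|
| 6 only | 28.9% (12 of 42) | 74.4% | 0.29 |
| 6 and 9 | about 5.5% (2 of 42) | 72.8% | about 0.195 |
| 3, 6 and 9 | about 3.8% (under 2 of 42) | about 73.5% | about 0.21 |

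Adding blocks of three lowers certainty a little further but does worse on the other two measures.

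**5. Cost in balance.** With sizes 6 and 9, about 27% of lists cut at 42 miss 28:14. Exercise ranges from 26 to 30, and misses are nearly always by one. Under the plan's SDs the standard error is √(196/28 + 4/14) = 2.70 at 28:14, √(196/26 + 4/16) = 2.79 at 26:16 and √(196/30 + 4/12) = 2.62 at 30:12, a change of about 3% either way.

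**The case against.** The strongest reply is that this is a design choice, not an error. The list is computer-generated by an independent statistician, and allocation comes after screening. Many eligibility criteria are objective (biopsy, age, BMI, HbA1c, hepatitis B). The primary endpoint is a laboratory value. Blocks of six also guarantee the planned split. All of this stands, though a laboratory endpoint limits assessment bias rather than selection bias.

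Three stronger readings are tempting, and the documents do not support them.

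- **That the investigator will know 29% of assignments.** The figure is a ceiling for someone who logs every assignment in order and tracks block boundaries. Nothing shows that this happens. Most of the certain places are exercise, already a two-in-three guess; only about 3 of the 12 are controls.
- **That mixed blocks remove most of the predictability.** They remove most of the certainty. An enroller can also steer on probabilities, and there the gain is modest: best guess falls by under two percentage points and predictable variance by about one third.
- **That assignments are released before eligibility and baseline are settled.** Section 7.2 randomizes after screening, and its post-consent baseline list includes the laboratory tests and MRI-PDFF. The gap is confined to VO2 max, DXA, waist, hip and skinfold measures.

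No size of bias in PAI-1 or in type I error can be derived from the documents, and none is claimed.

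**Conclusion.** The point holds as a worthwhile, low-cost improvement to the design. As written, up to 28.9% of assignments are deducible with certainty by an observer who knows the block size and all earlier assignments in order, and the last place of each block is always among them.

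This rests on three readings of the documents. The trial is treated as unmasked, inferred from the nature of the arms and the absence of any masking text. It is treated as single-site, because the multi-site section is marked not applicable. Six is treated as the only block size, because no other is given. Whether predictability would lead to actual selection is unknown.

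The separate timing point is narrow but real. VO2 max testing depends on the subject's effort, and Section 7.2 has it done once the arm may be known.

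**What to change.** 1. Have the independent statistician generate the 2:1 list with randomly varying block sizes, for example 6 and 9. If enrolment has begun, do this for the assignments still to be made.
2. Keep the sizes in a document restricted to that statistician, and have Section 7.2 say only that permuted blocks of varying size are used. Deleting the block size alone would not be enough, because the present text already discloses it.
3. Complete baseline VO2 max, DXA, waist, hip and skinfold measures before the assignment is released, and say so in Section 7.2 and the visit schedule.

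Items 1 and 2 cost a few lines of code and a short text change. The price is the guarantee of 28:14: about 27% of lists would end elsewhere, with 26 to 30 in exercise, at the small cost in precision shown above. Item 3 changes the order of assessments already planned for every subject and adds none.

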7.2 Study Procedures

Subjects will be invited for initial consultation performed by the study PI. This will be completed at the GCRC. If subjects are not currently in the Penn State system, they will be registered prior to this consultation through the Penn State Gastroenterology/Hepatology clinic staff ([name] or [name]). For all individuals who provide signed, informed consent, the following baseline measures will be completed:

- Comprehensive history and physical examination
- Anthropometric assessment [height, weight, BMI calculation]
- Physical activity questionnaire (IPAQ)
- Urine Pregnancy Test
- Nutrition counseling will be provided by a Registered Dietitian (RD) to promote a hypocaloric, low-fat dietary intake pattern. In the case that Dietitians are unavailable in person, counseling will be completed by phone or video chat using the Penn State Health-branded Zoom. Food Frequency Questionnaire (FFQ) will be used to assess their current dietary practices. Individual caloric needs will be calculated at baseline using the Mifflin St. Jeor equation, providing resting energy expenditure (REE), multiplied by the appropriate activity factor (AF) to yield total energy expenditure (TEE). Adjusted body weight (ABW) will be used when the participant's BMI is equal to or greater than 30. Five-hundred to 750 calories will be subtracted to promote an approximate weight loss of 1 pound per week for participants whose BMI classifies as overweight or obese. Macronutrient distribution will be recommended at 50-60% carbohydrate, 15-20% protein, and 20-30% fat with <10% total calories attributable to saturated fat. A sodium intake of <2,000 mg daily will be encouraged.

ABW & IBW Calculations:

- Use ABW to calculate REE when BMI ≥ 30
 - ABW calculation:
 - Males: $IBW + 0.38 \times (BW - IBW)$
 - Females: $IBW + 0.32 \times (BW - IBW)$
 - IBW calculation:
 - Males = $106 + 6 \times (Ht.(in)-60)$
 - Females = $100 + 5 \times (Ht.(in)-60)$

REE via Mifflin St. Jeor Equation:

- Male: $10(wt. (kg)) + 6.25(ht. (cm)) - 5(age (yr)) + 5 = REE \times AF = TEE$
- Female: $10(wt. (kg)) + 6.25(ht. (cm)) - 5(age (yr)) - 161 = REE \times AF = TEE$

| Activity Factors: | |
|--|--|
| Lifestyle and Physical Activity Level (PAL) | |

| | |
|--|---------------------|
| Seated work with no option of moving around and little or no strenuous leisure activity | 1.4-1.5 |

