| Seated work with discretion and requirement to move around but little or no strenuous leisure activity | 1.6-1.7 |
| Standing work (e.g. housework, shop assistant) | 1.8-1.9 |
| Significant amounts of sport or strenuous leisure activity (30-60 min four to five times per week) | +0.3 (increment) |
| Strenuous work or highly active leisure | 2.0-2.4 |

Creatin
g a Caloric

Deficit for Weight Loss:

- Male and Female:
 - TEE - 500 kcals when BMI 25-29.9
 - TEE – 750 kcals when BMI 30-44.9
- Fasting laboratory testing (including baseline assessment of the hemostatic system). Subjects will be instructed to be fasting for at least nine hours. The following tests will be performed:
 - Complete blood count
 - Hemoglobin A1c
 - Thromboelastography
 - Insulin level
 - Basic metabolic panel
 - Hepatic panel
 - Lipid panel
 - Ferritin
 - ADAMTS13
 - Plasminogen activator inhibitor one
 - D-dimer
 - VonWillebrand Factor
 - Protein C
 - Protein S
 - Factor VII
 - Factor VIII
 - INR
 - Fibrinogen
 - Antithrombin
 - P-selectin
 - Adiponectin
 - Cytokeratin-18
- Calculation of non-invasive markers of fibrosis [NAFLD Fibrosis Score, Fibrosis-4 Index (FIB-4)
- Stool sample collection for 16S ribosomal microbiome assessment. A home stool collection kit and instructions will be provided to the subject. The kit will be labeled with the subject’s study code number.
- Additional genetic testing for single nucleotide polymorphisms (SNPs) of interest for exercise response, coagulation or NASH; subjects will not be notified of the results of these tests.
- Assessment of hepatic fat content with MRI-PDFF
- Baseline electrocardiogram (ECG) to be reviewed by study physicians
- HRQOL assessment via the PROMIS-CAT, an individual approach tailored to the health status of each subject offering significant improvements over the existing fixed length questionnaire evaluations of HRQOL (e.g. Short Form-36) that have been used almost exclusively in NASH (<http://www.nihpromis.org>). (51, 79-90) PROMIS includes gender- and age-matched normative data obtained from extensive testing of the U.S. population. PROMIS will be completed in-person under the direct supervision of trained study personnel.
- The liver biopsy obtained prior to enrollment will be reviewed by the pathology department to confirm the stage of fibrosis and NASH Activity Score.

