Following their assessment and randomization, subjects will undergo baseline VO2 max testing at the Penn State Physical Medicine and Rehabilitation (PMR) Research Laboratories under the supervision of ACSM certified trained fitness professionals and study physicians. Anthropometric measurements will be completed at this assessment as well with dual-energy x-ray absorptiometry (DXA) body composition measurement, waist circumference, hip circumference and skin fold measurement. Following this, subjects will be given a Fitbit Charge2 with heart rate (HR) monitor along with an instruction form on how to use dietary log. Formal instruction on how to use the Fitbit Charge2 will be provided by trained study staff. This will include technical support with the Fitbit app that is supported on smartphones, the Fitbit website and Fitabase, a secure comprehensive data management platform for research studies, clinical trials and healthcare innovation projects utilized by >400 clinical trials since its inception. Participants will be instructed to record their food and beverage intake in a daily food diary through the Fitbit app and be provided information on how closely their daily food intake met the goals for macronutrients and energy.

Moderate intensity aerobic exercise: Subjects in the aerobic exercise group will be supervised to exercise 30 minutes, five times per week at a moderate intensity (HR target corresponding to 45-55% of their VO2max). Formal exercise instruction and supervision will be provided by ACSM certified fitness professionals at the Penn State University Fitness Center. Subjects will initiate their exercise program by walking on a treadmill for 15 minutes at their target HR goal and progressively increase the duration and frequency until the goal of 30 minutes of moderate intensity exercise five times a week is reached by the end of the four-week lead-in period. Subjects will then exercise five times a week under direct supervision in one of three locations; the Penn State University Fitness Center, the Cancer Center

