Control condition (standard of care). Subjects in the control condition will be instructed to continue their medical care at the discretion of their treating medical professional. They will be informed to maintain their current physical activity level. They will be given information from the American Liver Foundation to provide a basic understanding of NASH and to reinforce the counseling from their treating medical professional. We expect this information may result in a subject choosing to exercise, however, similar information-only interventions have led to only small effects, which are accounted for in the sample size calculation. Weekly phone calls will be performed by study personnel to ensure adherence to the protocol (no changes in activity). Subjects will report to Penn State on a monthly basis for anthropometric assessment in the GCRC to confirm their self-reports and study investigators will perform an interim history and physical examination at that time. Subjects may choose to complete this visit in person or virtually using Zoom. Subjects will also be given a Fitbit Charge2HR and downloaded data review will be performed monthly at study visits. These methods of compliance have previously been validated.(91)

This study will be a delayed treatment trial. Subjects randomized to the control condition will be given five months of fitness center membership to UFC and access to an ACSM certified fitness professional for training sessions following completion of the study protocol.

Penn State PM&R Research Laboratories: Housed at Hershey Center for Applied Research (HCAR), the 4,500 ft² facility is comprised of Exercise, Body Composition, Locomotor Training and Gait Laboratories

(Director-[name], collaborator). While the available exercise and body composition assessment equipment totals well over \$1,000,000 and includes multiple gait training devices, this study will utilize the following exercise equipment: Cosmed® K4B2 Portable Metabolic Device and ECG Telemetry system, ParvoMedics TrueMax® 2400 Metabolic Measurement System, and Quinton Q710 Stress Testing/Resting ECG System. Body composition resources include Lunar iDXA® DXA scanner, skinfold and anthropometric calipers.

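### Baseline VO2 max, an effort-dependent test to exhaustion, is done after randomisation, and nothing says the assignment is withheld until the value is recorded

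*Combined protocol and SAP*

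**What the plan says.** Section 7.2 gives the sequence in three steps.

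- A list of measures for every consented subject is introduced by "For all individuals who provide signed, informed consent, the following baseline measures will be completed". It includes "Plasminogen activator inhibitor one", the other haemostatic markers, MRI-PDFF, PROMIS, height, weight and BMI. VO2 max is not on it.
- Then comes allocation: "Once subjects have passed screening, they will be randomized 2:1 into either the exercise or control group respectively". An independent statistician generates the scheme by computer in blocks of six.
- Then comes the fitness test: "Following their assessment and randomization, subjects will undergo baseline VO2 max testing". DXA is done at the same visit, and the measurements there are given as "body composition measurement, waist circumference, hip circumference and skin fold measurement".

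The baseline test has a use in the intervention. The exercise-arm intensity is given as "HR target corresponding to 45-55% of their VO2max".

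The schedule of visits at the end of 7.2 puts VO2 max and DXA under the initial assessment on Day 0 and again at week 20. It has no row for randomisation. Section 11.0 says that the maximal test is continued to exhaustion and lists fainting, chest pains and falls among its risks.

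**The concern.** A baseline should be fixed before anyone can know the arm. VO2 max is read by equipment (section 7.2 names the "2400 Metabolic Measurement System"), but the equipment records what the subject does and cannot make the subject reach a maximum. A subject who knows the assignment might try harder or less hard, and a tester who knows it might encourage differently. ACSM certified fitness professionals supervise the test, and professionals with the same certification deliver the exercise programme.

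Two things would be at stake. First, the baseline VO2 max itself: it defines the exercise heart-rate target, no other VO2 max test is scheduled before exercise starts, and it would enter any analysis of change in fitness. Second, the randomised set: a subject who cannot complete the test, or in whom it reveals a reason for exclusion such as active cardiac symptoms (section 3.2), has already been randomised and counts under the intention-to-treat analysis in sections 3.3.2 and 8.3.

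**Working it through.** **Order of events.** The text of 7.2 runs: consent and listed baseline measures, randomisation, baseline VO2 max. The schedule does not reverse this. Its Day 0 column holds both the listed measures and VO2 max, and with no randomisation row it fits either order. The sentence in 7.2 is the only text that fixes the sequence.

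**Safeguards.** The only allocation safeguard described is the computer-generated scheme from an independent statistician. That governs how the sequence is made, not who knows the assignment at the test. No rule on the timing of disclosure, and no blinding of testers, is given.

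**Which measures are exposed.**

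| Measure | Listed before randomisation? | Depends on effort? | Use |
|---|---|---|---|
| PAI-1 and other haemostatic markers | Yes | No | Primary endpoint and secondary endpoints 1 to 5 |
| MRI-PDFF | Yes | No | Secondary endpoint 4 |
| PROMIS | Yes | Not a fitness test | Secondary endpoint 6 |
| VO2 max | No | Yes | Heart-rate target; secondary endpoint 5 if analysed as change |
| DXA | No | No, read by instrument | Body composition |
| Waist, hip, skinfold | No | Little | No named endpoint |

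Secondary endpoint 5 in section 1.3 correlates VO2 max with haemostatic markers after 16 weeks. Endpoint 4 speaks of changes in the markers; endpoint 5 does not. It can be read as a correlation of end-of-programme values, which needs no baseline.

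**Size of an effort effect.** This cannot be derived. The documents give no mean, standard deviation or expected difference for VO2 max.

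**What one loss costs in power.** Inputs from section 8.2: difference 9 ng/mL, SD 14.0 (exercise) and 2.0 (control), two-sided alpha 0.05, unequal-variance t-test.

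SE = √(14²/n₁ + 2²/n₂), noncentrality = 9/SE, power from the noncentral t distribution with Satterthwaite degrees of freedom.

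The plan's own figure first. At n₁ = 22 and n₂ = 11, SE = √(8.909 + 0.364) = 3.045, noncentrality = 2.956, df = 22.7 and power = 80.74%. This matches the stated figure, so the stated power corresponds to 33 evaluable subjects rather than to the 28 + 14 = 42 enrolled.

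| Exercise / control | Power |
|---|---|
| 28 / 14 | 89.7% |
| 28 / 13 (one control lost) | 89.6% |
| 27 / 14 (one exercise subject lost) | 88.5% |
| 22 / 11 | 80.74% |
| 21 / 11 (one further exercise subject lost) | 78.8% |

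From full enrolment, one loss costs 0.1 or 1.1 points (89.66 − 89.59; 89.66 − 88.54). Once planned attrition has been used up, one more exercise-arm loss costs about 1.9 points (80.74 − 78.79). These are the costs of any dropout, whatever the cause, and do not measure this particular weakness.

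**The case against.** The strongest case against is that little in the plan rests on this value. No endpoint in sections 1.2 or 1.3 is a between-arm comparison of change in VO2 max, endpoint 5 may need no baseline, and section 8.3 names no VO2 max covariate. The heart-rate target applies to one arm only, so it cannot distort a comparison of targets between arms. This stands, and it limits the consequence. It does not remove the reason to protect a baseline that sets the intensity of the intervention.

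A second objection is that silence is not disclosure. This also stands. A reader might infer that subjects and testers know the arm at the test, or that the baseline is biased. The documents support neither; they show only that nothing prevents it.

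A third is that losses are provided for. Section 8.2 expects 15–20% attrition, both arms take the test, and the history, examination, ECG and exclusion criteria should make losses at this step uncommon. That is fair. A reader might also infer from section 3.3.2 that withdrawn subjects give no week-20 PAI-1, because it mentions a phone call. The call is only an example, and the same section says that withdrawn subjects are followed at the same time points. Whether their PAI-1 is collected is a separate question from the order of tests.

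Finally, the supervised programme means that subjects know their arm at the week-20 test whatever is done at baseline. This is correct: a change score would remain open to arm-dependent effort at that end.

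**Conclusion.** The point holds as a modest design improvement. Section 7.2 states an order in which an effort-dependent baseline follows randomisation, with no rule delaying disclosure, and a better order is available at almost no cost. The bias is possible, not shown; its size and direction cannot be estimated from the documents. It bears on the exercise-arm heart-rate target, on any analysis of change in fitness, and on endpoint 5 only if that is analysed as change.

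The primary endpoint's baseline is not affected, and the documents do not support reading this as a threat to the primary result. Loss of randomised subjects at this step may be nil, and a single loss has little effect on power under the SDs assumed in section 8.2. The conclusion rests on taking the sentence in 7.2 as the intended order. If the Day 0 column was meant to place the test before randomisation, that sentence is what needs correcting.

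**What to change.** In section 7.2, have baseline VO2 max completed and recorded before randomisation. The DXA, waist, hip and skinfold measurements can move with it for convenience, since they share the visit; the concern for them is slight. In the schedule, add a randomisation row placed after these Day 0 measures.

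If scheduling prevents this, add one sentence: the assignment will not be disclosed to the subject or the testers until the baseline VO2 max has been recorded. That sentence covers the effort concern but not a loss after randomisation.

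It would also help to state in section 1.3 whether endpoint 5 uses week-20 values or changes.

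The cost is a change of order or one sentence, plus one schedule row, with no extra test or visit and no change to sample size or power. The downside is that an occasional subject will be tested but not randomised. The change protects the baseline only; it does nothing for effort at the week-20 test.
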